7.3 Unscheduled visits

Data from unscheduled visits will not be summarized in combination with the data from the scheduled visits. However, the data will be used to for shift tables and determine the safety assessments. Any measurement that indicates clinically significant abnormal values either from clinical or laboratory evaluations, will be considered for safety assessment.

7.4 Windowing Conventions

The following table describes assignment of visit windows to the following data for purposes of analysis:

Document: Document path and title

Template No.: RWI_TP_BIOS0013 Revision 2 Reference: RWI_WI_BIOS0015

Table 1. windowing conventions

Visit assigned	Day	Window
Screening visit 1	-20	+5
Screening visit 2	-14	±2
Baseline	-1	None
Day 1	1	None
Day 2	2	None
Day 3	3	None
Week 1	8	±2
Week 2	15	±2
Week 3	22	±2
Week 4	29	±2
Week 6	43	±5
Week 8	57	±5
Week 10	71	±14
Week 12	85	±14
Week 26	183	±14
Week 52	365	±21
Week 78 (EOS)	547	±21

[figure not shown]
For any laboratory procedures it is expected a window of ± 24 hours. However, any laboratory exam/testing performed outside the specified window will be considered for data analysis purpose (shift tables and liver function).

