Troponin- I/Troponin T		Х					Х			Х		Х	Х	Х	Х	Х	Х
Virus Serology	Х												Χ	Χ	Χ	Х	Х
Urinalysis			X			Χ											
Electrocardiogram (ECG)	Х		Х				Х			Х		Х	Х		Х	Х	Х
Echocardiogram	Х						Х			Χ		Χ	Χ	Х	Χ		Х
Prophylactic Prednisolone			Х	Х	Х	Х	Х	Х	X	Х	Х	Х					
OAV101 Infusion				Х													
Developmental Milestone Checklist		x								X			Х	X	Х	Х	Х
Concomitant medications	Х	Х	Х	Х	Х	Х	Х	Х	Х	Х	Х	Х	Х	Х	Х	Х	X
Adverse events/SAEs	Х	Х	Х	Х	Х	Х	Х	Х	Х	Х	Х	Х	Х	Х	Х	Х	Х
Study completion information																	Х

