7.2 Baseline

Baseline is defined as the last non-missing measurements taken prior to reference start date (including unscheduled assessments) and after the study enrollment.

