7.5 Common Calculations

No statistical hypothesis testing is intended; therefore, only descriptive analysis will be summarized for the collected data. The results will be expressed as absolute frequencies and

Document: Document path and title

Template No.: RWI_TP_BIOS0013 Revision 2 Reference: RWI_WI_BIOS0015

percentages (%) for categorical variables. Percentages will be calculated over the number of patients with available (non-missing) data. Mean and standard deviation or medians and quartiles (25th–75th percentile) ranges will be described for continuous variables, along with the minimum and maximum values. The 95% CI will be calculated as appropriate. The count of missing observations will be provided in all tables.

For quantitative measurements, change from baseline will be calculated as:

Test Value at Visit X – Baseline Value

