	Notalgia paraesthetica [10072643]
	Pain [10033371]
	Pain threshold decreased [10066956]
	Paradoxical pain [10067055]
	Paraesthesia [10033775]
	Peripheral nervous system function test abnormal [10034591]
	Peripheral sensorimotor neuropathy [10056673]
	Peripheral sensory neuropathy [10034620]
	Radicular pain [10059604]

Document: Document path and title

Template No.: RWI_TP_BIOS0013 Revision 2 Reference: RWI_WI_BIOS0015

AESI	Search methodology (MedDRA version 25.0 or later) [MedDRA	
	Code]	
	Reflex test abnormal [10068273]	
	Reflexes abnormal [10038254]	
	Reversed hot-cold sensation [10073738]	
	Sensorimotor disorder [10062162]	
	Sensory disturbance [10040026]	
	Sensory ganglionitis [10066196]	
	Sensory integrative dysfunction [10048871]	
	Sensory level abnormal [10061567]	
	Sensory loss [10040030]	
	Skin burning sensation [10054786]	
	Slow response to stimuli [10041045]	
	Synaesthesia [10078814]	
	Temperature perception test decreased [10068015]	
	Tenderness [10043224]	
	Thermoanaesthesia [10068010]	
	Thermohypoaesthesia [10068009]	
	Tinel's sign [10052492]	
	Trichodynia [10079852]	
	Unresponsive to stimuli [10045555]	
	Vibratory sense increased [10068327]	

AESI: Adverse event of special interest; HLT: High Level Terms; PT: Preferred Terms; SMQ: Standardized MedDRA Queries

See Appendix 2 for handling of partial dates for AEs. In the case where it is not possible to define an AE as treatment emergent or not, the AE will be classified by the worst case; i.e. treatment emergent.

Document: Document path and title

Template No.: RWI_TP_BIOS0013 Revision 2 Reference: RWI_WI_BIOS0015

Page 23 of 45

The incidence of TEAEs and AESIs will be summarized. Descriptive summary statistics for the change from baseline in cardiac safety assessments (ECG, Echocardiogram, troponin), clinical laboratory measurements (including hematology and liver function assessments), and vital signs will be summarized descriptively by visit/timepoint. A summary of all laboratorial assessments (including scheduled and unscheduled visits) will be summarized separately. Mean, standard deviation, median, minimum, and maximum will be presented for continuous variables. Categorical data will be presented as frequencies and percentages. For each applicable visit/timepoint, only participants with a baseline and a measurement for that timepoint will be included in the summary.

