15.1.6 CTC Grading for Adverse Events

AEs will be graded using the Common Toxicity grading (CTC) system version 4.03 as defined in the following link:

https://evs.nci.nih.gov/ftp1/CTCAE/CTCAE 4.03/CTCAE 4.03 2010-06-

14 QuickReference 8.5x11.pdf

CTCAE Grade 0 will be assigned for all non-missing values not graded as 1 or higher. Grade 5 will not be used. For laboratory tests where grades are not defined by CTCAE version 4.03, results will be categorized as low/normal/high based on laboratory normal ranges, according to each center.

The following listings/summaries will be generated separately for hematology, and biochemistry tests:

 Listing of all laboratory data with values flagged to show the corresponding CTCAE version 4.03 grades if applicable and the classifications relative to the laboratory normal ranges

For laboratory tests where grades are defined by CTCAE version 4.03:

- Worst post-baseline CTCAE grade (regardless of the baseline status). Each participant will be counted only once for the worst grade observed post-baseline.
- Shift tables using CTCAE version 4.03 grades to compare baseline to the worst ontreatment value

For laboratory tests where grades are not defined by CTCAE version 4.03:

Shift tables using the low/normal/high/ (low and high) classification to compare baseline
to the worst on-treatment value. Definition of low and high worst post-treatment values
were considered as follows:

Document: Document path and title

Template No.: RWI_TP_BIOS0013 Revision 2 Reference: RWI_WI_BIOS0015

o For all post-baseline visits (including unscheduled visits), in cases where the laboratory result is outside the normality range (i.e. <LLN or >ULN), the greatest deviation from the normality range will be considered as the worst post-treatment value. That is, if the largest deviation from normality is <LLN, the patient will be considered as "Low". If the greatest deviation is >ULN, the patient will be classified as "High". Cases where all post-baseline visits results are within the normal range will be classified as "Normal".

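### Do the overlapping Week 8, 10 and 12 windows in SAP Table 1 leave the by-visit safety summaries undefined?

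*SAP*

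**What the plan says.** SAP 7.4 opens Table 1 with "The following table describes assignment of visit windows to the following data for purposes of analysis" and heads its first column as the visit assigned. The rows at issue are Week 8 at Day 57 ±5, Week 10 at Day 71 ±14 and Week 12 at Day 85 ±14. Protocol Table 8-1 has the same days and tolerances as its visit schedule.

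Below the table the SAP adds "For any laboratory procedures it is expected a window of ± 24 hours". It says that laboratory results outside the window are still used for the shift tables and the liver-function analysis. It does not say what the 24 hours are counted from.

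Four other places bear on how a record gets its visit:

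- SAP 7.2: "Baseline is defined as the last non-missing measurements taken prior to reference start date".
- SAP 7.3: "Data from unscheduled visits will not be summarized in combination with the data from the scheduled visits".
- SAP 7.5 defines change from baseline as "Test Value at Visit X" minus the baseline value.
- SAP 15.3 confines laboratory change from baseline to scheduled visits.

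The summaries that depend on visit are those in SAP 15.1.1, where cardiac, laboratory and "vital signs will be summarized descriptively by visit/timepoint", and the matching items in SAP 15.3 and 15.4. In the public copy, the list that should follow the opening sentence of 7.4 and a figure below Table 1 are not shown.

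**The concern.** A table that says it assigns data to visits for analysis should place each record in one visit. This one does not. A Week 10 assessment on its exact target day, Day 71, also falls inside the Week 12 window. One on Day 85 is on target for Week 12 and still inside Week 10. A programmer working from study day alone would have to invent a tie-break, or could count a record at both visits.

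Change from baseline in vital signs, cardiac assessments and laboratory values is among the primary outcomes. Table 8-1 schedules vital signs, hematology, chemistry and liver tests, troponin and echocardiogram at all three visits, and ECG at Weeks 8 and 10. With about 15 children, one record is 1/15, or about 7%, of a visit row. An unwritten choice could therefore show in a primary safety table and in both interim readouts.

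**Working it through.** **Inputs.** Target days and tolerances are from SAP Table 1 and agree with protocol Table 8-1. The sample size of about 15 is from protocol 12.7.1.

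**Windows**, as target day minus and plus tolerance:

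| Visit | Calculation | Days | Length |
|---|---|---|---|
| Week 8 | 57 ± 5 | 52-62 | 11 |
| Week 10 | 71 ± 14 | 57-85 | 29 |
| Week 12 | 85 ± 14 | 71-99 | 29 |

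**Overlaps.** Weeks 8 and 10 share Days 57-62: 62 − 57 + 1 = 6. Weeks 10 and 12 share Days 71-85: 85 − 71 + 1 = 15. Weeks 8 and 12 share none. The three windows together cover Days 52-99, which is 48 days, so 6 + 15 = 21 of 48 are shared. The only other overlap in Table 1 is Screening 1 (Days −20 to −15) with Screening 2 (Days −16 to −12), on two days. It does not matter, because SAP 7.2 takes baseline as the last value before dosing, whatever its visit.

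**Is Table 1 meant to sort records by day?** After Day 3 its windows cover 5 + 5 + 5 + 5 (Weeks 1-4), 11 (Week 6), 48 (Weeks 8-12), 29 (Week 26), 43 (Week 52) and 43 (Week 78) days, a total of 194. From Day 4 to Day 568 there are 565 days, so 565 − 194 = 371 belong to no visit. A table that leaves most days unassigned and repeats the protocol's visit tolerances works as a check on timing, not as a way to sort undated-by-visit records.

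**Recorded visit.** If each scheduled record keeps its recorded visit, a Day 78 assessment entered as Week 10 is summarised at Week 10, once. The overlap then changes no row.

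**Would a written day-based rule do better?** Take nearest target day as a tie-break within Table 1. Days 57-62 go to Week 8, Days 71-77 to Week 10 and Days 79-85 to Week 12. Day 78 is 7 days from both 71 and 85, so it remains tied. Assessments validly done as Week 10 would be moved on 6 + 7 = 13 of its 29 permitted days, and those done as Week 12 on 7 of 29. That rule relabels valid visits and still needs another tie-break.

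**The 24-hour laboratory sentence.** Counted from the target day it gives Days 56-58, 70-72 and 84-86, which do not overlap. It would, however, leave 11 − 3 = 8 of 11, 29 − 3 = 26 of 29 and 26 of 29 permitted visit days outside the laboratory window. Counted from the visit, the sample follows the visit's label. Neither reading creates a new conflict between two scheduled visits.

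**The case for a change.** The strongest reply is that the wording of SAP 7.4 is explicit. It offers Table 1 as an analysis rule, and no sentence says that the recorded visit governs. SAP 7.3 separates scheduled from unscheduled data but does not choose between two scheduled visits. SAP 15.3 sends the reader to Section 7 for the handling of retests, and no such rule is visible there. All of this stands as a remark on drafting. It does not show that any record would be misplaced, because the scheduled/unscheduled split needs a recorded visit to operate at all.

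A second reply is that one SAP 15.3 item asks for a toxicity-grade shift by visit that includes unscheduled assessments, which carry no scheduled label. That is fair, but it concerns how unscheduled records are placed across the whole follow-up and would remain if these three windows did not overlap. SAP 15.1.6 also plans "Shift tables using CTCAE version 4.03 grades to compare baseline to the worst ontreatment value", which needs no visit assignment.

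Two smaller points also stand. The SAP does not say what the 24 hours are counted from. It also leaves open whether laboratory results outside that window enter the by-visit means or only the shift and liver tables. Neither arises from the overlap.

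**Conclusion.** The overlap is correctly observed, but it is missing detail that analysts will fill sensibly. Using the recorded visit is the ordinary choice, it fits SAP 7.3, 7.5 and 15.3, and it gives each scheduled record one place. Writing it down would change no planned result, and a day-based rule would be worse.

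At most, the placement of records at Weeks 8, 10 and 12 in descriptive by-visit rows is open, on 21 of 48 calendar days if study day alone were used. Days are not records, and the documents do not show how many assessments would fall there. TEAE and AESI incidence, worst post-baseline grades, liver-threshold counts and the Week 26, 52 and 78 milestones are untouched. SAP 7.5 plans no hypothesis test, and SAP 5.1 allows no design change from the interim readouts.

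The conclusion rests on two assumptions: that the eCRF labels each scheduled assessment with its visit, which the scheduled/unscheduled split requires, and that the material not shown beside Table 1 does not impose a different rule.

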7.5 Common Calculations

No statistical hypothesis testing is intended; therefore, only descriptive analysis will be summarized for the collected data. The results will be expressed as absolute frequencies and

Document: Document path and title

Template No.: RWI_TP_BIOS0013 Revision 2 Reference: RWI_WI_BIOS0015

percentages (%) for categorical variables. Percentages will be calculated over the number of patients with available (non-missing) data. Mean and standard deviation or medians and quartiles (25th–75th percentile) ranges will be described for continuous variables, along with the minimum and maximum values. The 95% CI will be calculated as appropriate. The count of missing observations will be provided in all tables.

For quantitative measurements, change from baseline will be calculated as:

Test Value at Visit X – Baseline Value

7.6 Software Version

All analyses will be conducted using Python version 3.6.9 or later, SAS version 9.4 or later, or a comparable statistical software package. The statistical software used will be reported at the final clinical study report.

8. STATISTICAL CONSIDERATIONS

8.1 Statistical Bias Reduction

As a prospective observational study, the main source of bias would be missing data. Handling missing data is described in the following sections.

8.2 Covariates and Factors captured in the study

The following covariates and factors are captured in the study and presented in the analyses:

- Demographic data:
 - o Gender
 - Age at study enrollment, in months
 - Age at OAV101 dosing, in months
- Medical history
 - Age at SMA diagnosis, in months

Document: Document path and title

Template No.: RWI_TP_BIOS0013 Revision 2 Reference: RWI_WI_BIOS0015

- SMA type (Type I, Type 2, Type 3A)
- Number of SMN2 copies
- Family history (carrier parents, siblings with SMA)
- o Previous SMA treatment (nursinersen, risdiplam), with start and end date
- Previous medical condition not related to SMA
- Hospitalization history (from birth until study enrollment)
- Examination
 - Height
 - Weight
 - o BMI
 - Physical examination
 - Neurological examination
 - Vital signs (systolic and diastolic blood pressure, pulse rate, respiration rate, body temperatures, SpO2)

Developmental Motor Milestone Checklist assessment

8.3 Missing data

The number of missing data will be reported for each variable of interest in the analysis. Missing data will be described separately, and no data imputation will be used.

Document: Document path and title

Template No.: RWI_TP_BIOS0013 Revision 2 Reference: RWI_WI_BIOS0015

Page 15 of 45

8.4 Sensitivity analysis

Given the descriptive nature of the summary of primary safety endpoints, no sensitivity analysis is planned.

9. OUTPUT PRESENTATIONS

The conventions for presentation of data in outputs is appended to this SAP (20.1. Appendix 1).

10. DISPOSITION AND WITHDRAWALS

All patients who provide informed consent and that received the OAV101 infusion will be accounted for in this study.

Patient disposition, withdrawals, and protocol violations (as defined in section 6.3), including inclusion and exclusion criteria will be presented for all enrolled patients.

11. DEMOGRAPHIC AND OTHER BASELINE CHARACTERISTICS

Demographic data and other baseline characteristics will be presented for the FAS. No statistical testing will be carried out for demographic or clinical characteristics. Only descriptive data will be reported (frequency, mean ± standard deviation, median, interquartile range, minimum and maximum).

Document: Document path and title

Template No.: RWI_TP_BIOS0013 Revision 2 Reference: RWI_WI_BIOS0015

Demographic characteristics:

- Date of birth
- Age at enrollment: calculated as time (in months) from date of birth to study enrollment (date of informed consent signature).
- Gender (female, male)
- Country (Argentina, Brazil)

Clinical characteristics at baseline

- Weight (kg)
- Height (cm)
- Body mass index (BMI) (kg/ m²)
- Systolic blood pressure (mmHg)
- Diastolic blood pressure (mmHg)
- Pulse rate (bpm)
- Respiration rate (breath per minute)
- Body temperature (°C)

Document: Document path and title

Template No.: RWI_TP_BIOS0013 Revision 2 Reference: RWI_WI_BIOS0015

Page 17 of 45

- Laboratory tests
 - o Hemogram
 - Chemistry/Liver function
 - Coagulation panel
 - o Troponin
 - Virus serology
 - Urinalysis
 - Electrocardiogram
 - o Echocardiogram

SMA medical history:

- Date of SMA diagnose
- Age at SMA diagnosis: calculated as the time (in months) from date of birth until SMA diagnosis
- SMA type: type 1, type 2, or type 3A
- Number of SMN2 copies: 0 until 5
- Carrier screening (yes/no)
 - Carrier parents (mother, father, both)
- Siblings with SMA (yes/no)
- Previous treatment for SMA (yes/no)
 - Nursinersen: start and end date of dosing, if applicable

Document: Document path and title

Template No.: RWI_TP_BIOS0013 Revision 2 Reference: RWI_WI_BIOS0015

Page 18 of 45

Risdiplam: start and end date of dosing, if applicable

11.1 Derivations

• BMI (kg/ m²) = weight (kg)/ height (m²)

12. CONCOMITANT MEDICAL CONDITIONS

Concomitant medical condition will be presented for the FAS.

Concomitant illnesses will be coded using MedDRA version 25 or later.

Concomitant medical conditions are those other than the indication being studied which started prior to or at Screening and are ongoing at the date of Screening.

Medical condition will be presented by SOC and PT.

13. MEDICATIONS

Medications will be presented for the FAS and coded using WHO drug dated March-2022 or later.

The Anatomical Therapeutic Chemical (ATC) class coding will follow level 3 structure.

See Appendix 2 for handling of partial dates for medications.

'Concomitant' medications are medications which:

- Started prior to, on or after the study medication dosing and started no later than
 30 days following end of study,
- AND ended on or after the date study medication dosing or were ongoing at the end of the study.

14. STUDY MEDICATION EXPOSURE

Exposure to study medication will be presented for the FAS.

Document: Document path and title

Template No.: RWI_TP_BIOS0013 Revision 2 Reference: RWI_WI_BIOS0015

Page 19 of 45

For the data analysis OAV101 will be considered as primary study medication and the corticosteroid as secondary study medication.

The date of OAV101 dosing will be taken from eCRF OAV101 infusion form.

The date of first corticosteroid administration will be taken from the eCRF Pre-infusion corticosteroid form. The date of last corticosteroid administration will be taken from the eCRF Prophylactic corticosteroid - Post-infusion details form.

Interruptions, compliance, and dose changes are not considered for duration of exposure and will be summarized separately.

15. PRIMARY OUTCOMES

15.1 Safety Outcome

All outputs for primary outcomes will be based on the FAS.

The primary outcomes are related to the safety assessments:

- Evaluation of treatment emergent AEs and SAEs
- Evaluation of important identified and potential risks
- Evaluate changes from baseline in vital signs, cardiac safety assessments, and clinical laboratory results

15.1.1 Adverse Events

Adverse Events (AEs) will be coded using MedDRA, Version 25 or later.

Treatment Emergent Adverse Events (TEAEs) are defined as AEs that started or worsened in severity on or after the OAV101 dosing through the last study visit.

Adverse events of special interest (AESI) are defined by the important identified risk an important potential risk as presented in the effective Risk Management Plan (RMP). The AESI will be summarized following the classification presented in Table 2.

Document: Document path and title

Template No.: RWI_TP_BIOS0013 Revision 2 Reference: RWI_WI_BIOS0015

Table 2: Adverse events of special interest classification

AESI	Search methodology (MedDRA version 25.0 or later) [MedDRA
	Code]
Hepatotoxicity	Hepatic disorders SMQ (Broad) [20000005]
Transient thrombocytopenia	Haemorrhages SMQ (Broad) [20000038]
	Haematopoietic thrombocytopenia SMQ (Broad) [20000031]
	HLT: Platelet disorders NEC [10035533]
Thrombotic microangiopathy	PTs:
	Thrombotic microangiopathy [10043645]
	Haemolytic uraemic syndrome [10018932]
	Atypical haemolytic uraemic syndrome [10079840]
Cardiac events	Cardiomyopathy SMQ (Broad) [20000150]
	Ischaemic heart disease SMQ (Broad) [20000043]
	Cardiac arrhythmias SMQ (Broad) [20000049]
	Embolic and thrombotic events SMQ (Broad) [20000081]
	Myocardial infarction SMQ (Broad) [20000047]
	Cardiac failure SMQ (Broad) [20000004]
	Hypertension SMQ (Broad) [20000147]
Sensory Abnormalities	PTs:
Suggestive of Ganglionopathy	Akinaesthesia [10051224]
	Allodynia [10053552]
	Anaesthesia [10002091]
	Anaesthesia dolorosa [10054878]
	Areflexia [10003084]
	Burning feet syndrome [10070237]
	Burning sensation [10006784]
	Central pain syndrome [10064012]

Document: Document path and title

Template No.: RWI_TP_BIOS0013 Revision 2 Reference: RWI_WI_BIOS0015

AESI	Search methodology (MedDRA version 25.0 or later) [MedDRA
	Code]
	Complex regional pain syndrome [10064332]
	Decreased vibratory sense [10067502]
	Discomfort [10013082]
	Dysaesthesia [10013886]
	Formication [10017062]
	Hyperaesthesia [10020568]
	Hyperpathia [10065952]
	Hypoaesthesia [10020937]
	Hyporeflexia [10021089]
	Hyporesponsive to stimuli [10071552]
	Intercostal neuralgia [10049949]
	Joint position sense decreased [10081223]
	Loss of proprioception [10057332]
	Nerve conduction studies abnormal [10029175]
	Nerve stimulation test abnormal [10029192]
	Neuralgia [10029223]
	Neuritis [10029240]
	Neurological symptom [10060860]
	Neuromuscular pain [10074313]
	Notalgia paraesthetica [10072643]
	Pain [10033371]
	Pain threshold decreased [10066956]
	Paradoxical pain [10067055]
	Paraesthesia [10033775]
	Peripheral nervous system function test abnormal [10034591]
	Peripheral sensorimotor neuropathy [10056673]
	Peripheral sensory neuropathy [10034620]
	Radicular pain [10059604]

Document: Document path and title

Template No.: RWI_TP_BIOS0013 Revision 2 Reference: RWI_WI_BIOS0015

AESI	Search methodology (MedDRA version 25.0 or later) [MedDRA	
	Code]	
	Reflex test abnormal [10068273]	
	Reflexes abnormal [10038254]	
	Reversed hot-cold sensation [10073738]	
	Sensorimotor disorder [10062162]	
	Sensory disturbance [10040026]	
	Sensory ganglionitis [10066196]	
	Sensory integrative dysfunction [10048871]	
	Sensory level abnormal [10061567]	
	Sensory loss [10040030]	
	Skin burning sensation [10054786]	
	Slow response to stimuli [10041045]	
	Synaesthesia [10078814]	
	Temperature perception test decreased [10068015]	
	Tenderness [10043224]	
	Thermoanaesthesia [10068010]	
	Thermohypoaesthesia [10068009]	
	Tinel's sign [10052492]	
	Trichodynia [10079852]	
	Unresponsive to stimuli [10045555]	
	Vibratory sense increased [10068327]	

AESI: Adverse event of special interest; HLT: High Level Terms; PT: Preferred Terms; SMQ: Standardized MedDRA Queries

See Appendix 2 for handling of partial dates for AEs. In the case where it is not possible to define an AE as treatment emergent or not, the AE will be classified by the worst case; i.e. treatment emergent.

Document: Document path and title

Template No.: RWI_TP_BIOS0013 Revision 2 Reference: RWI_WI_BIOS0015

Page 23 of 45

The incidence of TEAEs and AESIs will be summarized. Descriptive summary statistics for the change from baseline in cardiac safety assessments (ECG, Echocardiogram, troponin), clinical laboratory measurements (including hematology and liver function assessments), and vital signs will be summarized descriptively by visit/timepoint. A summary of all laboratorial assessments (including scheduled and unscheduled visits) will be summarized separately. Mean, standard deviation, median, minimum, and maximum will be presented for continuous variables. Categorical data will be presented as frequencies and percentages. For each applicable visit/timepoint, only participants with a baseline and a measurement for that timepoint will be included in the summary.

